On the other hand, there has been fewer research investigating the effects of manual treatment on trigger points. Travell and Simons initially treated trigger points with ischemic compression but later changed their recommendation to applying gentle digital pressure to trigger points ¹⁶. A recent study done on traction-compression-stretch technique compared with ischemic compression showed some, albeit minor, increased outcome measures (pain pressure threshold) warranting clinical investigation ⁶. (We can use their comparative model and statistics since it would be similar to our concept) Another study compared active release and muscle energy techniques in treating latent trigger points of the upper trapezius and found that both techniques were equally effective in increasing cervical range of motion and decreasing pain and upper trapezius thickness⁷. Other studies have also shown interest in similar osteopathic manipulative techniques such as counterstrain, myofascial release, facilitated positional release and high velocity-low amplitude thrust techniques in treating trigger points^{3,16-18}.

Studies have showed that the upper trapezius is one of the most common muscles affected by myofascial pain syndrome ^{19,20} leading to referred pain manifesting as headaches and stiff neck.

There is no consensus as to which treatment method is superior, with the decision to treat in a certain way/technique largely based upon the training received by the individual physician rather than the characteristics of the trigger point itself. There are currently no studies evaluating the efficacy of the various treatment options specifically osteopathic manipulative treatment vs. trigger point injections. Thus, the intention of the present study was to determine the efficacy rates of muscle energy techniques vs. dry needling in treating MTPs in the upper trapezius region.

Study Objective

The primary aim of this study is to observe whether osteopathic manipulative treatment or traditional lidocaine/dry needling technique is more efficacious or non-inferior and similar in treating myofascial trigger points in the upper trapezius region as it relates to quality of life and improvement in pain scores.

Study Design

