The study is a prospective cohort study comprised of participants between ages 25-75 presenting to Atlanticare Regional Medical Center interventional pain department and Philadelphia College of Osteopathic Medicine OMM Clinic between April 2021 and May 2021 with trigger point in the upper trapezius muscle. It is expected that approximately 60 patients will be enrolled to produce approximately 50 evaluable subjects.

Inclusion Criteria: The subjects will only be recruited into the study if they have met all the following criteria:

- Ages between 25 and 60 years.
- Previous or current diagnosis of MTrP in the upper trapezius region according to the criteria set by Simons et al.³
- 1 active/latent MTrP in the upper trapezius region

The diagnostic criteria to establish myofascial trigger point is adopted from Travell and Simons³ and include:

1. Presence of palpable taut band in the skeletal muscle
2. Presence of hypersensitive tender spot in the taut band
3. Presence of local twitch response upon stimulation of the taut band
4. Reproduction of referred pain upon palpation
5. Presence of spontaneous referred pain pattern

Exclusion criteria: Any subject that exhibits any of the following criteria will be excluded from the study:

- Pregnancy or immunocompromise
- Fever/infection
- Previous history of whiplash injury
- Previous history of cervical surgery, cervical radiculopathy, or myelopathy
- Severe disc or cervical lesion
- Evidence of cognitive deficit
- Degenerative or inflammatory disease of the cervical spine or shoulder, fibromyalgia, or neuromuscular diseases
- Use of medications (anticoagulants, anti-inflammatory etc.) or illicit drug use (1 week prior to treatment or follow up)
- Received treatment for MPS a month before the study recruitment

All the patients of interest that present to AtlantiCare Regional Medical Center pain clinic and Philadelphia College of Osteopathic Medicine OMM Clinic that meet the relevant inclusion and exclusion criteria will be invited to participate in this study. The subjects will be informed of the purpose of the study and asked for informed consent. If recruited into the study, they will be administered a pre-intervention survey. Subjects will then be managed according to standard of care by their point of care physician. Following the intervention they will be administered a post-intervention survey immediately following the intervention and one-week post.

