On the other hand, there has been less research investigating the effects of manual treatment on trigger points. Travell and Simons initially treated trigger points with ischemic compression but later changed their recommendation to applying gentle digital pressure to trigger points ²⁷. A recent study exploring the traction-compression-stretch technique (TTCE) compared to ischemic compression showed some, albeit minor, increased outcome measures (pain pressure threshold) warranting clinical investigation ⁶. Another study compared active release and muscle energy techniques in treating latent trigger points of the upper trapezius and found that both techniques were equally effective in increasing cervical range of motion and decreasing pain and upper trapezius thickness⁷. Other studies have also shown interest in similar osteopathic manipulative techniques such as counterstrain, myofascial release, facilitated positional release and high velocity-low amplitude thrust techniques for treating trigger points^{3,27-29}.

There is no consensus as to which treatment method is superior, leaving the method of treatment up to the discretion of the individual physician, rather than the characteristics of the trigger point itself. Often, determination of treatment method is dependent upon the training received by a physician. There are currently no studies evaluating the efficacy of these various treatment options, specifically osteopathic manipulative treatment vs. trigger point injections. Thus, the intention of the present study was to compare the efficacy of muscle energy techniques vs. lidocaine for the treatment of MTPs in the upper trapezius region.

Study Objective

The primary aim of this study is to compare osteopathic manipulative treatment and lidocaine injection technique for treatment of myofascial trigger points in the upper trapezius region.

Study Design

The study is a prospective cohort study containing of participants between ages 25-65 age range that presented to Atlanticare Regional Medical Center pain management clinic and Philadelphia College of Osteopathic Medicine Osteopathic Clinic between November 2021 and February 2022 with trigger point in the upper trapezius muscle.

Inclusion Criteria: Subjects were recruited into the study if they met all of the following criteria:

- Age between 25 and 65 years.
- Previous or current diagnosis of MTP in the upper trapezius region according to the criteria set by Simons et al.³

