The goal of this study was to demonstrate the efficacy of OMT, compared to lidocaine with dry needling injection techniques, in the treatment of trapezius MTP. The results of the study showed that both lidocaine with dry needling and OMT were successful in reducing pain related to myofascial trigger points. However, neither of the two techniques demonstrated discrete superiority to one another. Although, this was not an intent of the study. The primary outcome of interest was pain intensity levels. There was a larger degree of pain reduction in the OMT group immediately post-intervention whereas lidocaine with dry needling showed larger reduction in one-week post-intervention pain levels. In the wake-throes of an opioid epidemic, the search for suitable, effective alternatives that provide non-opioid treatment for pain are an added benefit in patient centered care.

When Travell and Simons first described the concept of myofascial trigger points, they proposed an 'integrated hypothesis' which included local myofascial tissues, genetics, neuromechanical and biochemical factors as precipitating factors in the formation of trigger points^{30,31}. In Travell's ATP energy crisis model³², triggers points were described as focal areas of hypoxia and thus OMT aimed at increasing oxygenation such as gentle traction and pressure release received acceptance. Various studies^{30,32-35} have demonstrated the utility of OMT in treating trigger points. As demonstrated in the results, OMT yielded significant reductions in pain intensity immediately post intervention and one week post intervention. The results of this study are in concordance with other similar studies. Although we hypothesized that OMT would be more as effective as lidocaine for treatment of MTP, we demonstrated that these two treatment methods both provide appropriate relief of musculoskeletal pain. This reflects the validity of OMT in the outpatient clinic, which is a suitable alternative for treatment of MTP. Equal efficacy of OMT for MTP treatment gives patients and physicians the option to elect for a non-invasive, low cost treatment.

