We specifically note that this is a suitable treatment modality for all physicians, both osteopathic and allopathic, as we merge our skill sets over time in a unified manner. As mentioned, the training of a physician usually dictates the management decisions regarding MTP treatment. This study was conducted in a post graduate training institution that has multiple specialty programs with osteopathic recognition. In the single accreditation system, collaborating with allopathic physicians and exposing allopathic residents to osteopathic treatment options was viewed an advancement for patient centered care and osteopathic awareness. As more allopathic physicians expand their skill sets and complete OMT courses, demonstrating the efficacy of a common treatment modality compared to OMT will assist with treatment choice. Comparable efficacy of both options will help patients choose the option that best meets their needs and physicians choose the option that best augments their skill set.

Being a pilot study, we anticipated a considerable degree of limitations throughout the study. Limitations include but are not limited to low sample size, majority female participants, and substantial difference in mean age between the two groups. Additionally, the OMT intervention group had a significantly lower mean pre-intervention pain level compared to the lidocaine group which made it difficult to do a true comparative analysis between groups. However, as a pilot study, demonstration of OMT non-inferiority compared to a standard treatment modality, creates a stepping stone for future research to investigate the comparative efficacy of OMT on a larger scale and we therefore anticipate future trials with larger number of participants to demonstrate more significant data and results.

Conclusion

Based on our study, OMT has comparable value with lidocaine injection technique as a treatment modality for active TrPs in the upper trapezius region. Both techniques demonstrate considerable decrease in pain intensity from baseline and thus it allows for increased collaboration between osteopathic and allopathic practitioners to promote patient centered care.

References

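### The SAP disclaims superiority, calls the study a pilot and claims non-inferiority without a margin, against the Protocol's aim and without reconciling its own significant interaction

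*SAP*

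**What the plan says.** **Protocol.** The Study Objective asks whether "osteopathic manipulative treatment or traditional lidocaine/dry needling technique is more efficacious or non-inferior and similar in treating myofascial trigger points". Superiority is the first option named; non-inferiority with similarity is the second. No margin is given. Under Study Design, "It is expected that approximately 60 patients will be enrolled to produce approximately 50 evaluable subjects". Data Analysis sets alpha at 0.05, without stating sidedness, and plans a 2 x 3 mixed ANOVA (treatment by three time points). The word pilot does not appear.

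**SAP.** The Study Objective is neutral: "The primary aim of this study is to compare osteopathic manipulative treatment and lidocaine injection technique for treatment of myofascial trigger points". Results reports the mixed ANOVA with a significant interaction, F(1.65, 56) = 3.90, p = .034, and rejects the null hypothesis. The Discussion then says that "neither of the two techniques demonstrated discrete superiority to one another. Although, this was not an intent of the study". It recalls the hypothesis in a form that cannot be read one way: "we hypothesized that OMT would be more as effective as lidocaine for treatment of MTP". It goes on to describe the two treatments as equally efficacious. Its limitations paragraph opens "Being a pilot study, we anticipated a considerable degree of limitations throughout the study" and later refers to "as a pilot study, demonstration of OMT non-inferiority compared to a standard treatment modality". Neither document contains a margin.

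**The concern.** A study cannot have superiority among the options of its primary aim and also not have intended to examine it. The denial and the pilot label both appear in a document that holds the results, after 31 of about 60 planned patients were enrolled (52%) and 30 of about 50 planned evaluable patients were analysed (60%).

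What is at stake is the conclusion. Dropping superiority leaves similarity as the only question, and the SAP then answers it favourably with no margin against which to judge it. A reader who sees the null rejected in Results and equal efficacy in the Discussion is given no way to connect the two. If the data are inconclusive, comparable value is the wrong summary.

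**Working it through.** **1. The SAP's between-group test.** With 30 patients in 2 groups, the uncorrected error df for the interaction is 2 x 28 = 56. A Greenhouse-Geisser numerator df of 1.65 goes with an error df of 1.65 x 28 = 46.2. The upper tail of F = 3.90 on (1.65, 46.2) df is p = .0345, in agreement with the printed .034. The printed error df of 56 is the uncorrected value and would give .033; the decision is the same.

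This test says that the two pain profiles over three times are not parallel. It does not locate the difference or give it a direction.

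**2. Are the within-group t values paired?** SAP Results calls them independent-samples tests, but the figures fit paired tests.
- OMM, one week: an independent test would give t = 0.95 / sqrt((1.84² + 2.01²)/21) = 0.95/0.595 = 1.60. The SAP prints 2.68 with 20 df, which is n - 1, and p = .014 (recomputed .0144).
- Lidocaine, one week: t = 2.16 gives p = .043 on the printed 20 df, .059 on 9 df and .063 on 8 df. The printed .062 fits 8 df, that is 9 patients.

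**3. One-week difference in change.** Inputs from SAP Results and Table 2: OMM 2.76 to 1.81, n = 21; lidocaine 7.00 to 4.00, n = 9. The SE of each mean change is the change divided by t.
- OMM: 0.95/2.68 = 0.354; SD = 0.354 x sqrt(21) = 1.62.
- Lidocaine: 3.00/2.16 = 1.389; SD = 1.389 x sqrt(9) = 4.17.
- Difference: 3.00 - 0.95 = 2.05, favouring lidocaine.

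| Method | SE | df | 95% CI | p |
|---|---|---|---|---|
| Welch | sqrt(0.354² + 1.389²) = 1.433 | 9.06 | -1.19 to 5.29 | .19 |
| Pooled (SD 2.616) | 2.616 x sqrt(1/21 + 1/9) = 1.042 | 28 | -0.09 to 4.19 | .059 |

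The larger variance is in the smaller group, so pooling understates the SE and Welch is the safer reading. The SAP itself reports unequal covariance matrices, and the ANOVA pools in the same way.

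**4. Immediate difference in change.** OMM 0.90 (t = 2.10, n = 21), lidocaine 0.40 (t = 1.17, n = 10): the reduction is 0.50 larger with OMM, Welch 95% CI -0.62 to 1.62, p = .37. The two contrasts point in opposite directions, and neither excludes zero.

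**5. Non-inferiority.** The one-week upper limits exclude only an OMM disadvantage of more than 4.19 (pooled) or 5.29 (Welch) points on a 0-10 scale.

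**6. Confounding.** Treatment is fixed by site (Protocol, Intervention). In SAP Table 1 all 21 OMM patients are aged 20-29, and 8 of 10 lidocaine patients are over 60. Baseline pain differs by 7.00 - 2.76 = 4.24 points. The OMM mean could fall by at most 2.76, less than the 3.00 seen with lidocaine. Raw one-week scores favour OMM by 4.00 - 1.81 = 2.19 (Welch p = .021), while change scores favour lidocaine by 2.05. The direction depends on how baseline is handled.

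**7. Limit of the recovery.** The lidocaine change SD implies a pre-post correlation of (3.04² + 2.17² - 4.17²)/(2 x 3.04 x 2.17) = about -0.26. With 9 patients that is possible but unusual, so the interval should be confirmed from patient-level data.

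**The case against.** Several stronger readings are tempting, and the documents do not support them.

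- *The primary question was never tested.* A reader might infer this from the disclaimer. But the mixed ANOVA planned in the Protocol was run, was significant and was used to reject the null. The fault is that the Discussion does not reconcile its conclusions with that result.
- *This was a superiority trial with a two-sided test, so similarity is a new question.* The Protocol's aim is disjunctive: "is more efficacious or non-inferior and similar in treating myofascial trigger points in the upper trapezius region". Similarity was always one branch, and sidedness is not stated.
- *The aim was changed after the data to hide a poor result.* The SAP's disclaimer was plainly written with results in hand, but no motive is documented. The Protocol's cover date, 28 April 2022, also falls after the recruitment window in the SAP (November 2021 to February 2022), so dates alone do not prove that the aim was fixed before the data.
- *Readers are told nothing of the weakness.* The Discussion does say that superiority was not shown. It lists low sample size and the age difference, and concedes that the baseline gap hampered a true comparison.

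It is also fair to object that the 2.05-point interval comes from back-calculated SDs, depends on the paired reading, and is confounded. All of that stands. It limits the interval as an estimate of treatment effect, but it lends no support to equal efficacy or non-inferiority.

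**Conclusion.** The contradiction holds: the Protocol's aim includes superiority, and the SAP says superiority was not intended. The pilot label has no basis in the Protocol. The non-inferiority and equal-efficacy claims have no margin behind them and stand unreconciled beside a rejected null.

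On the SAP's figures, neither superiority nor non-inferiority at any margin below about 4 points is established at one week. The accurate conclusion is inconclusive. This rests on three assumptions: the t values are paired, the lidocaine df is 8, and a difference in change is a usable summary despite the imbalance in site, age and baseline pain. The textual contradiction and the absence of a margin need none of these assumptions.

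**What to change.** In the SAP Discussion and Conclusion:

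1. Delete the disclaimer about intent, and state that the Protocol's aim included superiority as well as non-inferiority or similarity, with no margin set.
2. Report the interaction together with the one-week difference in change and its 95% CI, computed from patient-level data with unequal variances. State beside it the confounding by site, age and baseline pain, and conclude that the comparison is inconclusive.
3. Remove the equal-efficacy and non-inferiority statements, or label them unsupported because no margin was set. Bring the comparable-value wording in the Conclusion into line.
4. Remove the pilot label, or mark it as applied after the data.
5. Do not write a single one-week hypothesis into the Study Objective as if it had been prespecified. Neither document makes one week primary, and the Protocol's aim also covers quality of life. Mark any focus on one week as post hoc.

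The cost is rewording and one interval from existing data. The downside is a less favourable statement.

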To investigate the treatment effect between groups across time, a mixed design two factor ANOVA was utilized. As expected, due to small sample size, heterogeneity of covariance matrices was detected. This is considered a limitation of the study. Also, since a repeated measures design was implemented across three time periods, Mauchly's test of sphericity was examined and found to be significant ($p = .042$). This indicates that sphericity cannot be assumed, so a Greenhouse-Geisser statistic was computed. A statistically significant interaction effect was detected, $F(1.65, 56) = 3.90, p = .034$. Due to p-value being less than 0.05, we can confidently reject the null hypothesis and accept the alternative hypothesis.

[figure not shown]
Table 1.

Sociodemographic Data	Mean (SD) or Number (%)		P value
	OMM (n = 21)	Lidocaine (n = 10)	
Sex (%), n = 31 (100%)	21 (100)	10 (100)	
Male, n = 7 (22.6%)	5 (23.8)	2 (20)	
Female, n = 24 (77.4%)	16 (76.2)	8 (80)	
Age, y			
Subjects from 20 – 29 y, n = 22 (71%)	21 (100)	1 (10)	
Subjects from 30 – 39 y, n = 1 (3.2%)	0	1 (10)	
Subjects > 60y, n = 8 (25.8%)	0	8 (80)	
Ethnicity			
Caucasian, n = 20 (64.5%)	11 (52.4)	9 (90)	
African American, n = 1 (3.2%)	1 (4.8)	0	
Latino or Hispanic, n = 4 (12.9%)	3 (14.3)	1 (10)	
Asian, n = 6 (19.4%)	6 (28.6)	0	
Pain Intensity			
Pre-intervention	2.76 (1.8)	7 (2.8)	
Post-intervention (immediate)	1.86 (0.9)	6.6 (2.3)	0.026
Post-intervention (one week)	1.81 (2.0)	4 (2.2)	0.062

Table 2.

	Group	Mean	Std. Deviation	N
Pre-intervention Pain	OMM	2.76	1.84	21
	Lidocaine	7.00	3.04	9
	Total	4.03	2.96	30
Post-intervention immediate pain	OMM	1.86	0.96	21
	Lidocaine	6.56	2.45	9
	Total	3.27	2.66	30
Post-intervention 1 week pain	OMM	1.81	2.01	21
	Lidocaine	4.00	2.17	9
	Total	2.47	2.27	30

Figure 1.

Discussion

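### The SAP concludes non-inferiority, equal efficacy and comparable value, but no margin was set, neither hypothesis was tested, and no between-group interval is reported

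*SAP*

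**What the plan says.** **Claims.** All are in the SAP. The Discussion states "Equal efficacy of OMT for MTP treatment gives patients and physicians the option" to choose a non-invasive treatment, and later "Comparable efficacy of both options will help patients choose the option that best meets their needs". Its limitations paragraph refers to "demonstration of OMT non-inferiority compared to a standard treatment modality". The Conclusion states that "OMT has comparable value with lidocaine injection technique as a treatment modality".

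**Plan.** The protocol's Study Objective names non-inferiority and similarity as possible findings, but gives no margin. Its Data Analysis is a 2 x 3 mixed ANOVA at alpha 0.05. The SAP's Study Objective is only to compare the two treatments. Its Data Analysis consists of t-tests and logistic regression. Both Data Analysis sections list confidence intervals among the values of interest.

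**Results.** The SAP gives within-group t-tests and one group-by-time interaction, F(1.65, 56) = 3.90, p = .034, for which "heterogeneity of covariance matrices was detected". It reports that "neither of the two techniques demonstrated discrete superiority to one another", and also: "There was a larger degree of pain reduction in the OMT group immediately post-intervention whereas lidocaine with dry needling showed larger reduction" at one week. The limitations paragraph says that the lower baseline pain in the OMM arm "made it difficult to do a true comparative analysis between groups".

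**The concern.** A non-inferiority or equivalence conclusion needs a margin fixed in advance and a confidence interval, or equivalent test, set against it. Neither document has these. The tests that were planned and run look for a difference, and failing to show superiority with one of them does not show equality. The Discussion nevertheless moves from no demonstrated superiority to equal efficacy.

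The SAP is also at odds with itself. Its Results reject the null hypothesis of no group-by-time interaction, and its limitations paragraph says a true comparison was difficult. The next sentence there claims that non-inferiority was demonstrated.

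This is the study's headline message, and it is addressed to patients and physicians choosing between the treatments. If the data are compatible with a large difference in either treatment's favour, readers are told something the study did not find.

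**Working it through.** **1. The plan's own figure.** With Greenhouse-Geisser degrees of freedom 1.65 and 1.65 x 28 = 46.2, F = 3.90 gives p = .0345. The printed error df of 56 gives .033. The reported .034 is reproduced. It is a test of difference.

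**2. Were the within-group tests paired?** The Results call them independent-samples tests. From the reported means and SDs, independent-samples t would be as follows.

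| Comparison | Independent t | Reported t | Paired df and p | Reported p |
|---|---|---|---|---|
| OMM, immediate | 1.99 | 2.10 | 20: .049 | .048 |
| OMM, one week | 1.60 | 2.68 | 20: .014 | .014 |
| Lidocaine, immediate | 0.34 | 1.17 | 9: .27 | .27 |
| Lidocaine, one week | 2.41 | 2.16 | 8: .063 | .062 |

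The figures fit paired tests. The printed df of 20 for lidocaine would give .256 and .043.

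**3. Difference in change.** The SE of change is mean change / t, and the SD of change is SE x sqrt(n). The difference is OMM change minus lidocaine change, so a positive value means less relief with OMM.

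*One week*
- OMM: 0.95/2.68 = 0.354, SD 1.62 (n = 21).
- Lidocaine: 3.00/2.16 = 1.389, SD 4.17 (n = 9).
- Difference: -0.95 + 3.00 = +2.05. Welch SE = sqrt(0.354² + 1.389²) = 1.433, df 9.06, 95% CI -1.19 to 5.29, p = 0.19.
- Pooled variance: CI -0.09 to 4.19, p = .059.

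*Immediate*
- OMM: 0.90/2.10 = 0.429, SD 1.96.
- Lidocaine, nine patients in Table 2: 0.44/1.17 = 0.376, SD 1.13.
- Difference: -0.46. Welch SE 0.570, df 25.2, 95% CI -1.63 to 0.71, p = 0.43.
- The t of 1.17 comes from all ten lidocaine patients. Using all ten gives -0.50 (-1.62 to 0.62).

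*Rounding.* Whole-number scores with sums and sums of squares of the falls of 19/95 and 20/72 (OMM, immediate and one week) and 4/12 and 27/219 (lidocaine, n = 9) reproduce the four printed p-values. The lidocaine t values come out at 1.18 and 2.17, against 1.17 and 2.16 printed. The intervals become -1.18 to 5.28 (one week) and -1.64 to 0.72 (immediate), so rounding is immaterial.

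**4. Raw scores (Table 2, Welch, OMM minus lidocaine).**
- Baseline: 2.76 - 7.00 = -4.24 (-6.65 to -1.83).
- Immediate: 1.86 - 6.56 = -4.70 (-6.6 to -2.8).
- One week: 1.81 - 4.00 = -2.19 (-4.00 to -0.38).

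**5. What a margin would have done.** On one-week change, only a margin above 5.29 points (Welch) or 4.19 (pooled) would be met. On immediate change, any margin above 0.71 would be met. Raw one-week score favours OMM outright. The verdict would depend on the time point, scale and margin, and none of these was fixed for such a claim.

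**6. Confounding and floor.** Treatment was set by site. All 21 OMM patients were aged 20-29, and 8 of 10 lidocaine patients were over 60 (Table 1). The OMM mean could fall by at most 2.76, less than the 3.00 seen with lidocaine.

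**7. Does the interaction refute equality?** Not firmly. The test pools unequal covariances, with the larger one-week change variance in the smaller arm. Covariances were rebuilt from the Table 2 SDs and the SDs of change. The correlations between immediate and one-week scores are not reported. They were assumed as -0.35 to 0.38 (OMM), paired with 0.10 to -0.57 (lidocaine), so that F is near 3.90. This returns numerator df 1.66 and a Mauchly p of about .043, close to the SAP's 1.65 and .042. With normal data and no interaction, the nominal 5% test rejects in about 11% to 15% of simulations. A test allowing unequal covariances gives p of about 0.07 to 0.23.

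**The case against.** The study is called a pilot. The SAP already discloses the small sample, the age difference, the lower OMM baseline and the unequal covariances. That stands, and the fix should build on those caveats. But disclosing limits does not turn an untested claim into a demonstration, and the Conclusion's wording carries no caveat.

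The two comparable phrases are looser than the non-inferiority and equality claims. The sentence on comparable efficacy can be read as describing the purpose of such research, and equal efficacy may rest on relief within each arm. This has some force. Still, relief within each arm is not a comparison between arms, and neither lidocaine within-group test was significant (p = .27 and .062).

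The SAP does not specify Welch, and the pooled one-week interval is narrower. It still reaches 4.19 points, so the conclusion does not change.

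The simulation rests on assumed correlations and on normal data for a bounded scale. That is fair. It is used only to avoid reading too much into the interaction; the main point does not need it.

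**Conclusion.** The concern holds. The absence of a margin, of a non-inferiority or equivalence test, and of a between-group interval in the text and tables is plain from the documents and needs no reconstruction. Figure 1 could not be seen.

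Non-inferiority is neither shown nor excluded. A one-week interval for difference in change from -1.19 to 5.29 on a 0-10 scale is too wide to show comparability, and at one week change and raw scores point in opposite directions. The significant interaction does not support equal efficacy, but it does not firmly refute it either.

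The change intervals assume that the reported t values are paired, which the printed p-values support. All estimates are unadjusted, and they do not separate treatment from site, age and baseline pain. The point must be fixed because it changes what the study concludes.

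**What to change.** 1. Remove the non-inferiority and equal-efficacy claims from the SAP's Discussion.
2. Replace the comparable-efficacy and comparable-value wording in the Discussion and Conclusion with a statement that comparative efficacy was not established.
3. Add: *Neither non-inferiority nor equivalence was tested, and no margin was prespecified.* This also answers the protocol's objective, which raised non-inferiority.
4. Report from patient-level data the between-group difference in change with its Welch 95% interval at both the immediate and one-week time points, labelled as descriptive pilot estimates.
5. Beside those estimates, extend the existing limitations: treatment is confounded with site as well as age and baseline pain; the OMM baseline mean of 2.76 limits how far that arm could fall; raw and change scores disagree in direction at one week; and the interaction p-value comes from a test that pools unequal covariances.
6. Do not add a margin now. A margin and decision rule belong in the protocol of a future trial.

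The cost is wording in four places, these short additions, and two intervals from data already held. The conclusion weakens from comparable to not established.
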